**Evaluator (institution): University of Nottingham Principal investigator(s): [name]** 

Figure 1: Projected Sample Flow-Chart (Consort Diagram³)

<sup>3 Flow chart template from Schulz, Altman, and Moher (2010).

**Evaluator (institution): University of Nottingham Principal investigator(s): [name]** 

Table 2: RCT Design Parameters

Trial type and number of arms		Two-arm, cluster randomised
Unit of randomisation		School
	fication variables if applicable)	N/A
Duimany autooma	variable	Reading achievement
Primary outcome	measure (instrument, scale)	Woodcock-Johnson IV Letter-Word Identification (Continuous)
	variable(s)	Reading achievement, Mathematics achievement, Visual acuity
Secondary outcome(s)	measure(s) (instrument, scale)	Woodcock-Johnson IV Word Attack (continuous); Woodcock-Johnson IV Applied Problems (continuous); logMAR (continuous)

#### Randomisation

The proposed design involves a randomised multi-level/hierarchical trial, with school level randomisation using a simple randomisation process. School assignment will be completed for all schools in autumn 2019 for a total of 100 schools (50 control, 50 treatment).

### **Participants**

All regular state primary schools (academies, free schools, and local authority managed) from the Bradford Metropolitan area with a reception class are eligible for inclusion. All children are eligible within the reception year for vision screening (as per standard practice). The main impact analysis will focus on children who fail the

vision screening test in the intervention group compared to those who fail the vision screening test in the control group. These children will be recruited through participating schools that have signed a Memorandum of Understanding (MOU).

### Sample size calculations

The trial has been designed to maximise the possibility of detecting a small effect size, within a specified geographical area. The power analysis involved a significant number of sensitivity analyses conducted with a range of assumptions (varying ICCs, pre-post correlation, number of schools, etc.) and software – in particular MLPowSim (Browne, Golalizadeh Lahi, & Parker, 2009), PowerUpR (Bulus, Dong, Kelcey, & Spybrook, 2018), and Optimal Design (Raudenbush, 2011). The analyses discussed below use PowerUpR, which provides a more precise estimate than the more limited options available in Optimal Design. Our power calculations are detailed in

3 below.

Table 3: Sample Size Estimates

Table 5: Sample Size Estimates		OVERALL	FSM
MDES		0.195	0.22
	level 1 (student)	$0.88^{4}$	0.88
Pretest/ posttest correlations	level 2 (class)	-	-
	level 3 (school)	0.62	0.62
Intracluster correlations (ICCs)	level 2 (class)	-	-
intractuster correlations (ICCs)	level 3 (school)	0.155	0.15
Alpha		0.05	0.05
Power		0.8	0.8
One-sided or two-sided?		Two-sided	Two-sided
Average cluster size		76	3
	Intervention	50	50
Number of schools	Control	50	50
	Total	100	100
	Intervention	350	150
Number of pupils	Control	350	150
	Total	700	300

<sup>4 Villareal (2015) undertook a test review of the WJIV standard battery of tests and found correlations in the range of .83 -.95. In the Woodcock Johnson IV manual, test-retest correlations were between 0.83–0.95 for the age 7–11 group (p. 94). However, these sort of test-retest reliability analyses tend to be over very short periods (e.g., one day).

<sup>5 We have selected an ICC of 0.15 as this represents a trade-off in that the schools are centred on a specific small geographical region, but on the other hand recognises that some EEF trials amongst early years have been higher at 0.17–0.19.

<sup>6 15% of the average primary school year group of 47. We estimate that around a third of the pupils will be on FSM (DfE, 2019).

#### Outcome measures

The outcome measures for the primary and secondary outcomes are the Woodcock-Johnson IV Letter-Word Identification, the Woodcock-Johnson IV Word Attack, Woodcock-Johnson IV Applied Problems (Schrank, McGrew, & Mather, 2014), and logarithm of Minimum Angle of Resolution (logMAR). The measures have been selected as they satisfy What Works Clearing House standards (WWC, 2017). Specifically, the tests demonstrate face validity and reliability; are not overaligned with the intervention, and will be administered in the intervention and control groups in the same manner. These standardised performance-based measures are widely used and have been used previously in large-scale trials with a similar age group (Corcoran & Ross, 2014; Corcoran, & Ross, 2015; Corcoran, Ross, Irby, Tong, Lara-Alecio, & Guerrero, 2015).

The Woodcock-Johnson IV Tests of Achievement were internationally normed across multiple age groups (McGrew, LaForte, & Schrank, 2014). Letter-Word Identification is designed to test reading and decoding. Each pupil is provided with visual (i.e., text) stimuli and are required to identify printed letters and words. The response is oral, that is letter names and words. Letter-Word Identification was chosen as the primary outcome measure based on prior research with a similar population (Bruce et al., 2018a). Applied Problems tests quantitative knowledge, mathematical achievement, and quantitative reasoning. Pupils are provided with auditory questions and visual (i.e., numeric and text) stimuli and are required to perform mathematics calculations, providing an oral response comprising of numbers and words. Finally, Word Attack is designed to test reading decoding, auditory processing, and phonetic coding. The stimuli are visual (i.e., words) and pupils are tasked to read phonically and provide pronunciations of pseudo words (McGrew et al., 2014, pp. 127–128). For the analyses, raw scores will be converted to age-standardised scores.

The Keeler crowded logMAR test is the recommended test for performing vision screening in young children. VA will be measured at a three-meter distance using the LogMAR Crowded Test (Keeler, Windsor, UK), with four letters per line, and each letter designated a score of 0.025; therefore, the score total per line represents 0.10 log unit. (The lower the score the higher the VA). A matching card is used when testing children ages 4 to 5 years, therefore knowledge of letters is not a prerequisite for test performance.

Pre and posttests will be conducted based on one-to-one tests carried out in schools by UoN appointed staff, with training will be provided prior to pretest and posttest data collection. Demographic data will be collected along with supplementary data from the National Pupil Database to check for data quality, as well as to provide updates on FSMever for the KS1 follow-on study.

The evaluator will conduct all major evaluation aspects, including random assignment, collection, and analysis and reporting of data for the impact analysis. The PI has discussed with the developer the importance of adherence to the EEF independence evaluation guidelines.

### Analysis plan

The primary analysis focuses on reading achievement measured by the Woodcock-Johnson IV Letter-Word Identification scale. This will be administered in summer 2021, in addition to three secondary outcomes – reading achievement measured by the Woodcock-Johnson IV Word Attack scale; mathematics achievement measured by the Woodcock-Johnson IV Applied Problems scale; and VA measured by the logMAR.

The proposed analyses are summarised next and will be detailed separately in the statistical analysis plan.

### MAIN OUTCOME

The analysis of the main outcome will be conducted on an ITT basis. The varying intercept model is as follows:

$$\begin{aligned} y_{ij} &= \beta_{0j} + \beta_1 Treatment_{ij} + \beta_2 Pre - Test_{ij} + u_{0j} + \epsilon_{ij} \\ \\ u_{0j} \sim \mathcal{N} \left( 0, \sigma_{School}^2 \right) \\ \\ \epsilon_{ij} \sim \mathcal{N} \left( 0, \sigma_y^2 \right) \end{aligned}$$

This can be understood as follows. The posttest score for the  $i^{th}$  student in the  $j^{th}$  school is equal to the grand mean score  $(\beta_{0j})$ , the impact of a binary indicator denoting treatment received  $(\beta_1)$  which is coded as 0 or 1, the impact of the mean-centred normally distributed pre-test  $(\beta_2)$ , the school-level error term  $(u_{0j})$ , and finally the student-level error term  $(\epsilon_{ij})$ . The two error terms each receive their own probability distribution which are normally distributed and centred on 0, with the two variance parameters estimated from the data  $(\sigma_{school}^2)$  and  $\sigma_{y}^2$ .

Effects sizes will be calculated using Hedges g. This is calculated as the mean difference between the treatment and control group and divided by the square root of the total variance. The equation is presented below:

$$ES = \sqrt{\frac{Y_{Treatment} - Y_{Control}}{\left(\sigma_{School}^{2} + \sigma_{y}^{2}\right)}}$$

### **SUBGROUP ANALYSIS**

Additional models will be fitted, which will include the 'FSM ever' entitlement (defined as any student who has ever been classified as in receipt of free school meals). This will be fitted as an interaction model in the following form:

$$\begin{aligned} y_{ij} &= \beta_{0j} + \beta_1 Treatment_{ij} + \beta_2 Pre - test_{ij} + \beta_3 FSM_{ij} + \beta_4 FSM * Treatment_{ij} + u_{0j} + \epsilon_{ij} \\ \\ u_{0j} \sim \mathcal{N} \left( 0, \sigma_{School}^2 \right) \\ \\ \epsilon_{ij} \sim \mathcal{N} \left( 0, \sigma_y^2 \right) \end{aligned}$$

#### **SECONDARY OUTCOMES**

The three secondary outcomes: Woodcock-Johnson IV Word Attack scale, Woodcock-Johnson IV Applied Problems scale, and logMAR will be modelled in the same manner as the primary analysis based on intention to treat and estimate effect sizes using the same formula as above. Should there be a significant effect on both the Woodcock-Johnson and VA measures, we will conduct a follow-on analysis investigating the mediating impact of VA on academic outcomes.

Should there be a significant treatment effect on both the Woodcock-Johnson and VA measures, we will conduct a follow-on analysis using the Baron and Kenny (1986) approach modelled via multivariate Bayesian response model investigating the mediating impact of VA on academic outcomes (see Yuan & MacKinnon, 2009).

## **Implementation and Process Evaluation**

UoN will implement a robust fidelity of implementation protocol that evaluates adherence to GiC, and explicitly focuses on objective fidelity of implementation measures. The evaluation plan includes questions that provide information about for whom and under what conditions intervention impacts are observed. These questions address the fidelity of implementation (RQ1/2), change of teacher and Vision Coordinator use of strategies to encourage wearing of glasses (RQ3/4), perceptions of GiC amongst school senior leadership, VCs, teachers, and parents (RQ5), unintended consequences (RQ6), and finally, the recommendations for scale-up (RQ7). The research questions for the process evaluation are presented below:

## Research questions

- 1. To what extent are key components of *Glasses in Classes* implemented with fidelity across intervention schools? And what are the key factors that facilitate and hinder the implementation of Glasses in classes with fidelity across intervention schools?
- 2. What percentage of Glasses in Classes intervention schools have high fidelity of implementation according to the fidelity of implementation protocol?
- 3. What strategies to teachers use to encourage the wearing of glasses, in (high/low fidelity) intervention and control schools?
- 4. What strategies do Vision Coordinators' use to encourage wearing of glasses?
- 5. How do head teachers, vision coordinators, teachers and parents perceive the effectiveness of Glasses in Classes?
- 6. Are there any unintended consequences of Glasses in Classes in the intervention group?
- 7. What types of structures and partnerships need to be in place to help deliver Glasses in Classes to large numbers of school at scale?

Observable indicators that map to the key components of GiC logic model in Figure 2 will be used to evaluate the fidelity of implementation. Key component data will be collected throughout the trial. Table 4 outlines the key indicators including school vision coordinators attendance at training sessions (recorded using attendance logs), glasses ordered (recorded using optometrists' payment receipts for the dispensing of glasses), and provision of intervention in classrooms for children prescribed glasses. Criteria representing school level performance will be used to rate fidelity of implementation and investigate the extent to which GiC is implemented as intended for the treatment schools. For indicators, as defined in a fidelity matrix, a school-level fidelity of implementation threshold will be defined. Aggregate fidelity scores will be calculated for the key components by computing the schools with high fidelity of implementation.

Furthermore, the implementation and process evaluation will include six case studies of schools to investigate how GiC schools change their processes and practices to increase student achievement and mitigate vision-related barriers to learning. These samples will comprise three higher fidelity schools and three lower fidelity schools, selected from treatment schools based a qualitative judgement between developer and evaluator on school engagement, reported participation, and willingness to participate.

Another feature of the process and implementation evaluation will include measurement of stakeholders' perceptions of GiC. To investigate perceptions about GiC, teacher surveys will be administered online via Qualtrics at three time points (prior to the start of the intervention for the reception year, at the start of Year 1 due to COVID-19 and finally post-intervention at the end of Year 2), and parent and VC surveys following the intervention. Some aspects of the IPE use a sequential design and so the design of post-intervention Vision Coordinator surveys will be based on findings from the case study interviews. IPE data is summarised in Figure 2: Glasses in Classes Logic Model

**Evaluator (institution): University of Nottingham Principal investigator(s): [name]** 

#### 4 and Error! Reference source not found.5.

The post-intervention IPE will be conducted between May and July 2021 and will follow a mixed-method approach, including: i) a total of 15 semi-structured interviews with 6 SLT representatives, 6 vision coordinators, 2 community opticians, and the programme's developer; ii) 3 mixed (qualitative & quantitative) surveys, administered through the online platform Qualtrics, with teachers (intervention and control schools), parents (intervention and control schools), and vision coordinators; iii) a total of 6 case studies with 3 low-fidelity vs 3 high-fidelity schools.

All interviews will be video or audio-recorded, with the permission of the study participants. The audio-recordings will be transcribed and anonymised. The survey data will be collected with the informed consent of the participants and anonymised.

The qualitative data (interview transcripts) will be analysed through employing a phenomenological psychological approach, where the focus is on exploring inductively the participants' authentic experiences of the GiC programme. Instead of relying on processes of categorising and quantifying things, phenomenology focuses on describing how things are experienced by the people directly involved (Denscombe, 2007) and is, therefore, suitable for the purposes of the IPE. Interview transcripts will be analysed through an inductive thematic analysis procedure (Braun & Clarke, 2006; King, 2004) and the qualitative data analysis software NVivo. A similar thematic analysis approach will be applied to the qualitative survey data.

The quantitative survey data will be analysed through SPSS. As with the pre-intervention surveys (2019), the analysis of the post-intervention data will focus mostly of the descriptive statistics of the key variables (e.g. participants' evaluations of various aspects of the programme, use of implementation strategies, etc.) and group comparisons (intervention vs control schools) where applicable.

In a departure from the original IPE design as a result of the COVID-19 pandemic, the following changes were made.

- Firstly the parental focus group was changed into a parental survey that will be deployed in all intervention schools to understand glasses wear at home and parental support strategies, as well as attitudes to the Glasses in Classes intervention. Running a focus group during a pandemic was considered too risky and electronic alternatives were considered unsuitable. This data will be used to address RQ5. The survey will be translated into Urdu and Punjabi in order to increase engagement, using the standard functionality in Qualtrics. We will work closely with schools to align dissemination of the survey to parents with typical approaches (e.g. email, text, paper)
- Secondly, vision coordinators will be interviewed in the six cases study schools and then surveyed in all intervention schools. Given that importance of the vision coordinators role in monitoring and promoting glasses wear in schools, this will be a very useful addition to provide more data to address RQ4, RQ5, RQ6 and RQ8. Preliminary analysis of the VC interviews will inform the design of the VC survey. This will be circulated in late June
- Thirdly, to better understand the changes to the delivery of glasses into schools to better promote the uptake of glasses, the community optometry teams and the developer will be interviewed to understand testing and dispensing of glasses directly in schools, the cost effectiveness of the approach and potential structures and partnerships needed to deliver at scale. This data will be used to address RQ7 and RQ8.

[figure not shown]
<sup>7 Denscombe, M. (2007). *The good research guide for small scale social research projects* (3rd ed.). Berkshire, UK: Open University Press.

<sup>8 Braun, V., & Clarke, V. (2006). Using thematic analysis in psychology. Qualitative Research in Psychology, 3, 77–101; King, N. (2004). Using templates in the thematic analysis of text. In C. Cassell & G. Symon (Eds.), Essential guide to qualitative methods in organizational research (pp. 11–22). London: Sage.

**Evaluator (institution): University of Nottingham Principal investigator(s): [name]** 

Figure 2: Glasses in Classes Logic Model

<sup>9 Text in dashed line rectangles represents hypothesised long-term outcomes not measured in the current trial.

**Evaluator (institution): University of Nottingham Principal investigator(s): [name]** 

Table 4: Fidelity Matrix Glasses in Classes Treatment Schools 2019–2021

Indicators	Definition	Unit	Source	Collection of data 	Thresholds for fidelity of implementation	Adequate implementation threshold
Key Component 1: Schools - Professional Development Indicator	1-day group training over 12- months	Vision Coordinators	Attendance Logs	UoL/BIHR	0 = No vision coordinator attends one day training 0.5 = Vision coordinator views a recording of the one day training 1 = Vision coordinator attends one day training – in person or online	Implementation with fidelity = Score of 1 Percentage with a score of 1
Key Component 2: Families Indicator	Attend optometrist with prescription	Parent/Primary care giver	Attendance logs	UoL/BIHR	Percentage attendance:  0 = <80% Attend optometrist with prescription 1 = 80-89% Attend optometrist with prescription. 2 = 90-100% Attend optometrist with prescription	Implementation with fidelity = Score of 2 (i.e., attend optometrist with prescription) Percentage with a score of 2
Key Component 3: Health - Materials Indicator	Each child receives two pairs of personal glasses	Child/school	Optometrist payment receipts for the dispensing of glasses	UoL/BIHR	0 = No glasses 1 = Incomplete set (e.g., one pair) 2 = Full set (two pairs)	Implementation with fidelity = score of 2  Percentage of children with a score of 2

-

<sup>10 UoL – University of Leeds and BIHR (delivery team), UoN – University of Nottingham (evaluation team)

**Evaluator (institution): University of Nottingham Principal investigator(s): [name]** 

Table 5: Implementation and Process Evaluation Measures

Outcome Measure	Instrument	To whom it is administered	Who administers	Date
Detailed information on glasses wearing and availability of eyeglasses	Online survey administered via Qualtrics	98 Teachers	UoN	05/21
Training session rating of quality	Brief online survey administered via Qualtrics	49 VCs at treatment schools	UoN	11/19 09/20
Training session quality	Observations of two training sessions using observation rubric	49 VCs at treatment schools	UoN	11/19
Parent perceptions of GiC	Brief online survey administered via Qualtrics and distributed by schools	770 parents (intervention and control schools) – provided in English, Urdu and Punjabi	UoN	06/21
Head teacher perceptions of Glasses in Classes	Six semi-structured interviews conducted via Teams to examine perceptions and reactions to GiC	6 Head teachers in case study schools	UoN	05/21
Vision coordinators perceptions of GiC	Six semi-structured interviews conducted via Teams to examine the perspectives and reactions to implementing GiC	6 VCs in case study schools	UoN	05/21
VCs' perceptions of GiC	Brief online survey administered via Qualtrics	49 VCs at treatment schools	UoN	06/21
Business-as-usual control and treatment diffusion	Online survey of control school administered via Qualtrics	49 school contacts in the control group	UoN	11/19 09/20 05/21
Cost Evaluation	Online survey administered via Qualtrics	Programme developer	UoN	07/21
Community optician team perceptions of GiC	Two semi-structured interviews conducted via phone/Zoom/MS  Teams to examine the perspectives of testing and dispensing glasses within schools vs. high street facilities.	2 opticians involved in year 2 testing and dispensing of glasses in schools	UoN	07/21
Developer's perception of GiC	One semi-structured interview conducted via Teams to examine the experience of the developers in the design and implementation of Glasses in Classes	Programme developer	UoN	07/21

### Cost evaluation

The GiC costing information will be collected from the developer at the end of the study. Costing will account for the total programme implementation excluding the evaluation costs. Information provided will include:

- (i) the average cost per child for the school glasses (GiC);
- (ii) the average cost per child for breakages and/or loss of the school glasses;
- (iii) the no. of contacts by health team liaising (phone or visit) with the vision co-ordinator in addition to the planned monthly feedback;
- (iv) the no. of contacts the vision co-ordinator for each school has with parents to follow-up glasses wear.

The cost per year per school will be calculated based on the total number of schools that participate in the trial as outlined in EEF cost guidance (EEF, 2015). The total cost per student will be estimated according to the number of students in the treated school per year and for each of years 1 and 2 of the intervention. Cost ratings will be based on an approximate cost of GiC implementation per year per pupil.

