#### **Risks**

Business-as-usual schools will not be exposed to GiC intervention prior to study completion. Control schools will only receive business-as-usual services and supports. Threats to the delivery of the trial will be minimised via the following mechanisms:

- 1. Project delivery team will explain ramifications of participating in a randomised controlled trial to the school partners.
- 2. Schools will be required to sign an MOU indicating they are willing to participate in a randomised controlled trial and agree to the terms of contract agreement.

An online survey of control school will be used to monitor any potential treatment diffusion. However, it is not anticipated that the confounds outlined will take place in this study.

Other risks include loss of evaluation staff. However, the University of Nottingham has a large experienced staff team with ample expertise available as needed. Another risk includes failure to recruit an adequate number of schools. The timeline for recruitment is brief, given that schools will need to be in a position to have been randomised and the intervention promoted by mid-October in the 2019/20 academic year. To mitigate this risk, we suggest to over-recruit schools. Similarly, the work in September and October 2019 will be a short time scale to ensure that glasses can be ordered and delivered for the beginning of January 2020. Our process evaluation includes a robust fidelity of implementation protocol to minimize this risk. The risk analysis is presented below in **Error! Reference source not found.**6.

Table 6: Risk Analysis

Risk	Likelihood	Impact	Contingency plan
Inadequate schools recruited and reduced power	Moderate	Moderate	Compensation will be given to schools for completing pre and post-tests (£750 for controls and £250 for treatment groups). All schools are required to sign an MOU in spring 2021.
Different opinions on study design	Moderate	Moderate	UoN staff are experienced evaluators and work with intervention developers flexibly and expeditiously to ensure the study design is robust and meets standards for independence.
Data protection	Low	High	UoN have robust data protection and procedures in place

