Pre-test/ post-	level 1 (pupil)	0.88 ¹	0.88	0.88	0.88
test	level 2 (class)	-	-	-	-
correlations	level 3 (school)	0.62	0.62	0.62	0.62
Intracluster	level 2 (class)	-	-	-	-
correlations (ICCs)	level 3 (school)	0.15 ²	0.15	0.15	0.15
Alpha		0.05	0.05	0.05	0.05
Power		0.8	0.8	0.8	0.8
One-sided or two-sided?		Two-sided	Two-sided	Two-sided	Two-sided
Average cluster size		7	3	8	
	intervention	50	50	50	50
Number of schools	control	50	50	49	49
	total	100	100	99	99
	intervention	350	150	406	

¹ Villarreal (2015) undertook a test review of the WJIV standard battery of tests and found correlations in the range of .83-.95. In the Woodcock Johnson IV manual, test-retest correlations were between 0.83-0.95 for the age 7-11 group (p.94). However, these sort of test-re-test reliability analyses tend to be over very short periods (e.g. one day).

² We have selected an ICC of 0.15 as this represents a trade-off in that the schools are centred on a specific small geographical region, but on the other hand recognises that some EEF trials amongst Early Years have been higher at 0.17-0.19.

		Prot	Protocol		nisation
		OVERALL	FSM	OVERALL	FSM
Number of pupils	control	350	150	387	
	total	700	300	793	

With the above parameters, at the protocol stage, we estimated that it is possible to achieve an MDES of 0.195 for the main effect and 0.22 for FSM subgroup analysis. During recruitment we found that the number of children failing their initial vision screening was slightly higher than expected giving an average cluster size of 8 children in the study. Despite recruiting one school less than planned, the MDES remained effectively stationary at 0.194. The FSM estimate at randomisation will be updated once we receive the matched data from the DfE containing the FSM indicator.

Analysis

The analysis will examine the impact of the Glasses in Classes intervention in comparison to the business-as-usual control condition on the basis of intention to treat (ITT) using a two-level multilevel model using Maximum Likelihood estimation.

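### Cost per school is to be divided by the schools of both arms although only intervention schools generate programme cost; read literally, this about halves it

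*Protocol*

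**What the plan says.** The protocol's Cost evaluation section sets one numerator and two denominators.

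- Numerator: "Costing will account for the total programme implementation excluding the evaluation costs".
- Cost per school: "The cost per year per school will be calculated based on the total number of schools that participate in the trial". The sentence then refers to the funder's 2015 cost guidance.
- Cost per pupil: "The total cost per student will be estimated according to the number of students in the treated school per year", with a separate figure for each of the two intervention years.
- Rating: "Cost ratings will be based on an approximate cost of GiC implementation per year per pupil".

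On what the control arm receives, the Risks section says: "Control schools will only receive business-as-usual services and supports".

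The documents give three sets of school counts. The protocol's Randomisation section plans 50 treatment and 50 control schools. SAP Table 2 shows 50 and 49 at randomisation. Protocol Table 5 lists 49 vision coordinators at treatment schools and 49 control-school contacts. The SAP has no cost section, so nothing there refines the rule.

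**The concern.** Numerator and denominator do not cover the same units. The programme consists of training, spare glasses, in-school refraction and monitoring, and it is delivered in one arm only. The stated rule nevertheless counts every school in the trial. A school leader or funder who reads the published cost per school will take it as the cost of running the programme in one school. With near-equal allocation, the figure would be about half of that cost, and the programme would look cheaper to adopt than it is.

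**Working it through.** The documents state no cost figure, so there is nothing to reproduce. The size of the error can still be found, because the cost itself cancels.

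**Does the wording cover both arms?**

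- The Participants section describes children from both groups as coming through participating schools that signed a memorandum of understanding. The Risks section has schools sign it as agreement to take part in a randomised trial. In this protocol, participation in the trial therefore includes control schools.
- The next sentence of the Cost evaluation section refers to the treated school. The narrower term was available and was not used for the per-school rule.

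**Do control schools add anything to the numerator?**

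- They receive usual care only.
- Vision screening takes place in both arms, but the Participants section calls it standard practice, so it is not a programme cost.
- The payment to control schools in Table 6 is for completing the pre- and post-tests. I read that as an evaluation cost, which the numerator excludes.

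The control arm's contribution is therefore taken as zero.

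**Formula.** Let C be the programme cost, T the intervention schools and K the control schools.

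reported / cost per intervention school = [C / (T + K)] / [C / T] = T / (T + K)

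| Source | T | K | T / (T + K) | Understatement | Correct / reported |
|---|---|---|---|---|---|
| Protocol, Randomisation (planned) | 50 | 50 | 50/100 = 0.500 | 50.0% | 2.00 |
| SAP Table 2 (randomised) | 50 | 49 | 50/99 = 0.505 | 49.5% | 1.98 |
| Protocol Table 5 | 49 | 49 | 49/98 = 0.500 | 50.0% | 2.00 |

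The Table 5 row assumes one vision coordinator per treatment school and one contact per control school.

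**Per-pupil rule.** Had control pupils been counted, the same dilution would appear: 350/700 = 0.50 as planned, or 406/793 = 0.51 at randomisation. They are not counted, because the rule is confined to treated schools. Dilution by control pupils is nil, and correcting the per-school rule leaves the per-pupil figure unchanged.

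**What remains open in the per-pupil rule.** It does not say which pupils of a treated school count. The average year group is 47 (protocol, Design), and the pupils who fail screening average 7 per school as planned or 8 at randomisation (SAP Table 2). A cost per year-group pupil would be 7/47 = 15% to 8/47 = 17% of a cost per screen-failing pupil. That is the spread between two possible readings, not a demonstrated error.

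**The case against.** The strongest reply is that the authors probably meant delivering schools. The sentence defers to the funder's cost guidance, which is not available here and may restrict the count in that way. The inputs listed in the same section also concern the intervention: school glasses, their breakage or loss, and contacts with vision coordinators, who are trained in the intervention group only. No cost has yet been calculated, and no outcome analysis depends on one. All of this stands as evidence of intent. It does not change what the sentence says, and an analyst who follows the sentence gets the wrong number.

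A reader might infer two stronger points, and the documents support neither.

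- That the per-pupil cost has the same fault. It does not, because control pupils are outside its denominator. Saying that it is too low for another reason, by spreading cost over a year group or the whole roll, requires a meaning the text does not state. The listed per-child glasses costs point, if anything, towards children who have glasses.
- That the cost rating is halved. It is not, because the rating rests on cost per pupil per year and the per-school figure does not enter it.

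**Conclusion.** The concern holds for the per-school figure only. Followed as written, the rule reports about half the cost per intervention school, an understatement of 49.5% to 50% on every school count in the documents. This rests on two assumptions: that the wording is applied literally to both arms, and that control schools add nothing to programme cost. The documents support both, though the cited guidance might show that a narrower count was intended. The treatment-effect estimates, the per-pupil cost and the cost rating are unaffected. It is a wrong definition in a descriptive output and should be corrected before costs are reported. The undefined set of pupils in a treated school is a separate, secondary point that calls for clarification.

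**What to change.** 1. Replace the per-school sentence with a rule such as: cost per school per year equals total delivery cost in the intervention arm for that year, divided by the number of intervention schools in which the programme was delivered that year.
2. Reconcile the 50 intervention schools in SAP Table 2 with the 49 implied by protocol Table 5, and state the number delivering in each year. The divisor should not be fixed at 50 until this is done.
3. As a secondary clarification, say whether the per-pupil denominator means pupils served by the programme, the year group or the whole roll. If it means pupils served, include any joiners whose costs are counted. The Design section leaves joiners out of the analysis sample but gives them the intervention, so the 406 intervention pupils at randomisation need not match the pupils whose costs are in the numerator. Label any per-roll figure separately.

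The cost is a few sentences in the protocol and a yearly count of delivering schools, plus a count of joiners served if their costs are included. No new outcome data are needed. Compared with the literal rule, the reported cost per school rises by a factor of 1.98 to 2.00.
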